While almost all of the reviewed studies of at-risk youth in the meta-analysis and the systematic review were limited by their cross-sectional design, the results do hold promise for mentoring interventions that incorporate the positive characteristics of natural mentors (i.e., more of a friendship-like, ‘coach’, or ‘cheerleader’ role) for young people who have experienced homelessness. These findings are supported by a small ($n = 23$) qualitative study of natural mentoring relationships among homeless youth (ages 14 – 21) that suggests “natural mentors could feasibly serve as a bridge in a coordinated effort to assist youth out of homelessness” (Dang & Miller, 2013, p. 7).

From the limited research that has been done with young people transitioning away from homelessness, the emerging evidence seems to indicate that, while structural supports such as subsidized housing and social service providers are important, these things alone are insufficient to help young people integrate into mainstream society. As it currently stands, it appears as if the burden for achieving meaningful social integration is on the formerly homeless young people, who continue to be marginalized despite achieving stable or semi-stable housing (Quilgars & Pleace, 2016; Thulien et al., 2018). Connecting these young people with an adult who exhibits the relationship-based components of natural mentoring that young people value most (e.g., genuine interest in their well-being and belief in their ability to succeed, a non-judgmental attitude and a willingness to listen, the provision of advice, guidance, affirmation and encouragement) (Dang & Miller, 2013; Thompson et al., 2016; Van Dam et al., 2018) may be key to helping them move forward and integrate into the mainstream.

This intervention will provide 24 young people (ages 16 – 26) who have transitioned out of homelessness and into market rent housing within the past year with rent subsidies for 24 months. Half of the young people will also receive mentorship. We chose to focus on young people living in market rent housing because, due to limited subsidized housing options, this is the reality for most young people exiting homelessness.

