Initially, we proposed to our community partners a study design where only half the young people would receive rent subsidies, with the other half receiving ‘treatment as usual’; however, we abandoned this idea after our community partners challenged the ethics of not providing or delaying rent subsidies for young people living a precarious existence and desperate for immediate, tangible support to help them remain in market rent housing. Consequently, we adopted the stance that, given housing is a basic human right², we would offer rent subsidies to *all* of the study participants. While this does move us away from the ‘gold standard’ in terms of measuring the impact of rent subsidies on social integration, we believe the mixed methods longitudinal design will still yield important insights in this regard. Moreover, this design adaptation reflects our deep commitment to engage in community-based participatory action research (CBPAR) – a methodology that challenges traditional epistemological assumptions of what constitutes ‘good’ evidence, demands researcher humility, stresses genuine and equitable academic-community partnerships, and facilitates the undertaking of research in a way that the *community* feels is most beneficial to their members

² “Adequate housing is essential to one’s sense of dignity, safety, inclusion and ability to contribute to the fabric of our neighbourhoods and societies...without appropriate housing it is often not possible to get and keep employment, to recover from mental illness or other disabilities, to integrate into the community, to escape physical or emotional violence or to keep custody of children” (Ontario Human Rights Commission, n.d.).

(Goodkind et al., 2017; Wallerstein & Duran, 2006; Wallerstein, Duran, Oetzel, & Minkler, 2018).

Half of the young people will be randomized to receive regular mentorship from an adult mentor, tasked with helping their mentee bridge the gap between homelessness and mainstream living. While some of these mentors will not be ‘natural’ in the sense that these may not be pre-existing, organically-formed relationships (see 3a. Mentorship), the mentors will incorporate the key relationship-based components of natural mentoring mentioned previously, with a strong emphasis on a strengths-based approach (i.e., focus on the young person’s strengths as opposed to their limitations) and the connection of participants to larger social networks (including education and employment).

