The study will be conducted in three Canadian cities: Toronto, Ontario (pop. 2.8 million); Hamilton, Ontario (pop. 552,000); and St. Catharines, Ontario (pop. 133,000). The design and implementation of this study is very much collaborative effort between our research team and the following community partners: a) Covenant House Toronto; b) Living Rock Ministries; and c) The RAFT (St. Catharines).

All of the study participants ($n = 24$) will receive rent subsidies (ranging from \$400 – \$500/month)³ for 24 months. This study includes funding for the rent subsidies and will be paid directly to the landlords by our community partners. St. Michael’s Hospital will establish a service provider agreement with each of our community partners for this purpose.

3a. Mentorship

Participants in the intervention group ($n = 12$) will be matched with an adult mentor recruited by one of our community partners. Each of our community partners expressed a strong desire to take the lead in the screening and recruitment of mentors as they feel they are in the best position to work with the study participants to ensure the best mentor ‘fit’. Drawing on the expertise of our community partners and sharing decision-making power is aligned with CBPAR principles and highlights our commitment to collaborative, equitable partnerships in all phases of the research process (Israel et al., 2018). Moreover, working with established community resources makes practical sense; not only will this facilitate co-learning and capacity building between the research team and our community partners (Israel et al.), but delivering the mentorship intervention under ‘real world’ conditions will provide important insights into scalability and sustainability (Wallerstein & Duran, 2010).

³ Given the higher cost of rent in Toronto, youth living in Toronto will receive \$500/month, while youth living in Hamilton and St. Catharines will receive \$400/month.

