All of the study participants will be screened for eligibility (see criteria above) and recommended for the study by one of our community partners (Covenant House Toronto, Living Rock Ministries, and The RAFT). A member of the research team will call each recruited youth on the telephone and arrange to meet them at a location most convenient for the youth. Potential participants will be given a copy of the participant information and consent form to read. This document will also be reviewed verbally to ensure that those who have low literacy levels have been given the information required to give informed consent. During this process, the research team member will assess the capacity of the potential participant to provide free and informed consent. If it is unclear whether a youth is able to provide consent, the study co-investigator ([name]) will be contacted immediately. [name] will arrange for a qualified member of the research team to conduct a capacity assessment. If it is determined that a youth is not able to consent, they will be informed of this and they will be excluded from the study. The appropriate community partner will be notified as well.

3f. Allocation Procedure

[figure not shown]
If the participant meets the eligibility criteria, informed consent will be obtained, and the participant will be enrolled in the study. During this initial meeting, enrolled participants will participate in a baseline interview. There will be no unmasking of assignment prior to randomization. Following the baseline interview, participants at each of the three study sites (Toronto (n=12), Hamilton (n=6), and St. Catharine's (n=6)) will be randomized using block randomization to either the intervention (rent subsidies plus mentoring) or control (rent subsidies only) group. Randomization will be balanced by site based on random block sizes of two and four. The advantage of using block randomization is to uniformly distribute participants into treatment groups within each site (Efird, 2010). Because small block sizes may increase the risk of guessing the allocation procedure and subsequently introducing bias into the enrolment procedure, random block sizes will be used to avoid this potential selection bias (Suresh, 2011).

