A unique randomization schedule will be produced for each site using SAS (SAS Institute Inc., Cary, NC, USA), with the algorithm described in Efird (2010) and will be generated by a statistician based at St. Michael's Hospital. A research coordinator based at St. Michael's Hospital and not affiliated with the study will be the only person with access to the randomization schedule. The research coordinator will prepare sealed, opaque and sequentially numbered envelopes with the randomization results of participants. After assessing for eligibility and obtaining consent of each participant, research personnel responsible for enrolling participants will open the next randomization envelope from the sequentially ordered randomization envelope file to obtain the participant's randomized group assignment. Randomization envelopes for all sites will be held in a locked cabinet at Centre for Urban Health Solutions, St. Michael's Hospital. The research coordinator enrolling participants will record the participant's group allocation into the Participant Linking Log, record their Participant ID number onto the randomization envelope, and return all opened randomization envelopes to the independent research coordinator at St. Michael's Hospital. Subsequently, the independent St. Michael's research coordinator will complete the Master Randomization Assignment List with Participant ID numbers corresponding to each envelope number to check for consistency in participant allocation. Both the Participant Linking Log and Master Randomization Assignment List will be securely kept on St. Michael's Hospital servers.

Participants will be informed immediately if they have been allocated to the intervention or control group (Figure 1). In keeping with typical community-based RCTs with psychosocial interventions, 'blinding' in this study would not be pragmatic (e.g., social service providers and mentors will know if participants are in the 'treatment' group) after the baseline interviews and random assignments have been conducted (Solomon, Cavanaugh, & Draine, 2009).

Figure 1.

CONSORT (CONsolidation of the Standards Of Reporting Trials) Diagram of Ideal Flow of Participants Through the Study.

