One major critique of mixed methods RCTs is that, typically, there is no true integration (i.e., ‘mixing’) of quantitative and qualitative findings at the level of analysis or interpretation (Lewin, Glenton, & Oxman, 2009). Moreover, it is often unclear whether or how the quantitative and qualitative researchers have worked together to maximize the potential synergies between these different approaches (Lewin et al.). With this in mind, our study team, consisting of researchers with quantitative and qualitative expertise, worked together to develop this study protocol and anticipate meeting quarterly to discuss the emerging analysis and to explore (and follow up on) similarities or discrepancies between the quantitative and qualitative data.

5a. Quantitative Data

All analyses will be performed using the intention-to-treat principle; that is, all participants will be included and analyzed in the groups they were originally randomized. Baseline characteristics of the intervention and control groups will be summarized using descriptive statistics (i.e., mean, standard deviation, median and interquartile range for continuous variables, and frequencies and proportions for categorical variables). We will also calculate descriptive statistics for outcomes at each study time point, and will explore differences in trajectories from baseline to 30 months follow-up between intervention and control groups using scatterplots and box-plots. Differences with 95% confidence intervals in continuous outcomes at 18 months (psychological community integration, self-esteem, social connectedness, hope, perceived housing quality, psychiatric symptoms, and sense of engulfment) between participants who received rent subsidies plus mentorship and participants who only received rent subsidies will be estimated using Analysis of Covariance (i.e., linear regression models), including an indicator of intervention group and the baseline value of the outcome. We will perform regression diagnostics and will repeat analyses using the non-parametric Wilcoxon

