rank-sum test if there are extreme outliers or influential observations. Groups will be compared with respect to count outcomes at 18 months (physical community integration) using graphical tools and the non-parametric Wilcoxon rank-sum test. For binary outcomes at 18 months (sustained academic and vocational participation, and income above low income cut-off⁴), differences in proportions with 95% confidence intervals will be estimated and tested using the chi-square or Fisher's exact test. Given the small sample size of this pilot randomized trial, all results will be interpreted with caution and with the intention of generating data and hypotheses for conducting a larger trial.

All efforts will be made to reduce participants' attrition and drop-out. As mentioned previously, we believe our strong relationship with the outreach workers and community agencies will help minimize loss to follow-up (Slesnick et al., 2009). In addition, we have made it very clear in the participant information and consent form that participants in the rent subsidies plus mentorship arm may continue in the study (receiving only rent subsidies) if they are unable to continue in a mentor-mentee relationship.

5b. Qualitative Data

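### Randomisation is stratified by site but the ANCOVA leaves site out; if sites differ at 18 months beyond what baseline explains, the confidence intervals are wider than they need to be

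*Combined protocol and SAP*

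**What the plan says.** Section 3f (Allocation Procedure) gives the site sizes as "Toronto (n=12), Hamilton (n=6), and St. Catharine's (n=6" and stratifies the allocation: "Randomization will be balanced by site based on random block sizes of two and four". It also states: "A unique randomization schedule will be produced for each site using SAS".

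Section 5a (Quantitative Data) estimates the 18-month difference in each continuous outcome, with a 95% confidence interval, by ANCOVA, "including an indicator of intervention group and the baseline value of the outcome". This covers psychological community integration, self-esteem, social connectedness, hope, perceived housing quality, psychiatric symptoms and engulfment. Site appears nowhere in section 5a, either as a covariate or in a sensitivity analysis, and no reason is given for leaving it out.

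Footnote 3 to section 3 records one built-in difference between sites, the monthly subsidy: "Given the higher cost of rent in Toronto, youth living in Toronto will receive" $500, against $400 in Hamilton and St. Catharines. Section 5a also says: "Given the small sample size of this pilot randomized trial, all results will be interpreted with caution".

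**The concern.** Balancing the arms within site removes most between-site variation from the true sampling error of the treatment difference. A model without site does not know this. It leaves the variation in the residual, so the standard error it reports is too large whenever sites differ beyond what the baseline score explains. The design then takes the trouble to stratify and the analysis does not collect the benefit.

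At stake are interval width and power in a trial of 24, and the residual variance, which a pilot may pass on to the planning of a larger trial. Bias and false positives are not at stake.

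Baseline adjustment cannot absorb differences that start or grow after baseline. Several influences continue through follow-up in both arms: the subsidy amount, each agency's own outreach workers (section 3b), and cities ranging from 133,000 to 2.8 million people (section 3). These make later divergence plausible but do not establish it. The larger Toronto subsidy offsets higher rent, so it could widen or narrow outcome differences.

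**Working it through.** The documents state no power calculation, SD, baseline correlation, site variance or dropout rate, so there is no plan figure to reproduce.

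**Inputs from the documents.** N = 24, half per arm, sites 12/6/6, blocked within site, arm-plus-baseline ANCOVA, 95% intervals.

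**Assumptions.** Within-site SD of 1 at both times; within-site correlation r = 0.6 between baseline and outcome; true effect 1 SD; Toronto differs from the other two sites by c SD. Dropout, where used, is random.

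**Degrees of freedom.** The planned model has 24 − 3 = 21 (t = 2.080); with two site indicators, 24 − 5 = 19 (t = 2.093). With five dropouts these become 16 (t = 2.120) and 14 (t = 2.145).

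**Hand check, gap arising only after baseline, exact balance within site.**

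- The residual variance within site is 1 − 0.6² = 0.64.
- With site: SE = √(0.64 × 4/24) = 0.327; width = 2 × 2.093 × 0.327 = 1.37.
- Without site: the Toronto gap adds 24 × c²/4 = 6c² to the residual sum of squares, so the residual variance is about 0.64 + 6c²/21.
- At c = 1: 0.64 + 0.286 = 0.926; SE = √(0.926 × 4/24) = 0.393; width = 2 × 2.080 × 0.393 = 1.63.
- Coverage at c = 1: the true SE is still 0.327, so the effective multiplier is 2.080 × 0.393/0.327 = 2.50, which corresponds to about 97.9% coverage.
- Break-even: √(1 + 6c²/(21 × 0.64)) = 2.093/2.080 gives c ≈ 0.17.

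**Hand check, same 1 SD gap at baseline and at 18 months.** The pooled baseline–outcome covariance is 0.6 + 0.25 = 0.85 and each pooled variance is 1.25. The residual variance is 1.25 − 0.85²/1.25 = 0.672, barely above 0.64. The width ratio without/with site is √(0.672/0.64) × 2.080/2.093 ≈ 1.02.

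**Simulation** (20,000 runs per scenario, exact balance within site), mean width of the 95% interval:

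| Toronto gap | Dropouts | Without site | With site |
|---|---|---|---|
| None | 0 | 1.37 | 1.39 |
| 0.5 SD, after baseline only | 0 | 1.44 | 1.38 |
| 1 SD, after baseline only | 0 | 1.64 | 1.39 |
| 0.5 SD at baseline, growing to 1 SD | 0 | 1.50 | 1.39 |
| Stable 0.5 SD | 0 | 1.38 | 1.38 |
| Stable 1 SD | 0 | 1.41 | 1.39 |
| None | 5 | 1.59 | 1.64 |
| Stable 0.5 SD | 5 | 1.60 | 1.63 |
| 0.5 SD, after baseline only | 5 | 1.67 | 1.64 |
| 1 SD, after baseline only | 5 | 1.90 | 1.64 |

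With no dropout, the 1 SD post-baseline gap gives coverage of 97.9% without site and 95.0% with it, and power of 69% and 81%. The growing gap gives power of 76% and 81%; the stable 1 SD gap, 80% and 81%. The simulated break-even is about 0.2 SD, slightly above the hand value because the latter ignores chance correlation between the covariates.

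**Block truncation.** Random blocks of two and four (taken as equally likely) cut off at 12/6/6 leave at least one site not exactly balanced in about 32% of schedules. The estimate stays unbiased and the widths barely move: 1.65 against 1.39 for the 1 SD post-baseline gap, and 1.38 against 1.39 for no gap.

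**Second simulation** (r = 0.5, gap in residual SDs, random blocks). The ratio of width without site to width with site is 0.99, 1.02, 1.12 and 1.26 at gaps of 0, 0.5, 1.0 and 1.5. If only the two small sites differ from each other, it is 1.01, 1.06 and 1.13 at 0.5, 1.0 and 1.5.

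**The case against.** The strongest reply is that nothing here is invalid. The estimate is unbiased, coverage is essentially at or above 95%, and the trial is a cautious, hypothesis-generating pilot with no power target. A material loss needs a large site gap that is absent, or much smaller, at baseline, and the documents do not show one. Stable city differences are already mostly absorbed by the baseline score. With 24 people and two sites of six, a three-parameter model is defensible.

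Dropout strengthens this reply. The documents give no rate, but loss over 18 months is a real prospect in this population. With five dropouts:

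- Break-even rises to roughly 0.35 to 0.4 SD (width ratio with/without site 1.009 at 0.3 SD and 0.994 at 0.4 SD).
- With no site effect, adding site lowers power from about 70% to 67%.
- A stable 1 SD gap slightly favours leaving site out (1.616 against 1.627).

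With eight dropouts and no site effect, site costs about 5% in width, and a 0.5 SD post-baseline gap only breaks even.

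All of this stands, and it limits the point to a possible gain in precision. It does not remove the point: the cost of adding site stays small over these cases, while the possible gain is several times larger. Interpreting results cautiously does not correct a standard error that ignores how participants were allocated.

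**Conclusion.** The concern holds as a conditional and minor one. The mismatch between allocation and model is plain in the text; its consequence depends on site differences that the documents do not quantify. With no dropout or five, and under the stated assumptions, adding site changes interval width by anything from about 3% wider to about 16% narrower. The upper figure is the 1 SD post-baseline gap without dropout: the rounded widths, 1 − 1.39/1.64, give 15%, and the unrounded result is 15.8%. With heavier dropout the cost can exceed 3%. These are results for chosen scenarios, not bounds. Confidence in the direction is high; confidence that the gain would be material in this trial is only moderate.

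**What to change.** In section 5a, add site as a fixed effect (two indicators) to each ANCOVA, and keep the arm-plus-baseline model as a prespecified sensitivity analysis. Fix the choice before 18-month outcomes are compared by arm, so that it cannot depend on the results. No change to the Wilcoxon or binary analyses is asked for.

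The cost is one phrase, one extra analysis and two residual degrees of freedom. If site adds little beyond baseline, intervals widen by about 1% with no dropout and 2 to 3% with five dropouts. No new data and no change to trial conduct are needed. If heavy dropout is expected, reversing the roles, with the site-adjusted model as the sensitivity analysis, would be a proportionate alternative.

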We will draw on the following key principles of CBPAR as we generate and analyse data (Chenail et al., 2012; Rutman et al., 2005; Wallerstein & Duran, 2006; Wallerstein et al., 2018):

- Research participants are viewed as experts in their own lives
- Concerted effort to reduce/eliminate power imbalances between the researchers and the community
- Equal value placed on academic (researcher) knowledge and experiential (community agency/youth) knowledge

- Commitment to producing practical, ‘actionable’ data to build community capacity and improve/transform the lives of the research participants
- Duty to remain invested with the community beyond the life of the research project

3d. Participant Eligibility and Recruitment

Twenty-four young people ages 16 – 26 who have left homelessness within the past year and are living in market rent housing will be collaboratively recruited by our research team and our community partners Covenant House Toronto, Living Rock Ministries, and The RAFT (St. Catharines). We will aim to have a roughly even balance of gender and ethno-racial representation at each site.

In addition to the above age and housing **inclusion** criteria, study participants must:

- Be able to provide free and informed consent
- Be fluent in English
- Plan on staying in or nearby the community in which they were recruited (Toronto, Hamilton, or St. Catharines) for the duration of the 24-month study
- Be willing to be matched with an adult mentor who has been screened and recommended by one of our three community partners (Covenant House Toronto, Living Rock Ministries, or The RAFT) **Note:** Each study participant will be able to select their own mentor once the potential mentors have been carefully screened by our community partners (see attached *Covenant House Toronto Mentor Program: Initial Screening Application*; *Covenant House Toronto Mentor Program: Screening Interview*; and *Covenant House Toronto Mentor Program: Confidential Volunteer Reference Form*, which our partners in Hamilton and St. Catharines will adopt as well).

Young people will be **excluded** from the study if they are:

- In imminent danger of losing their housing (e.g., facing jail time or impending eviction)
- Enrolled in another study with enhanced financial and social supports

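### The outlier check on the continuous outcomes swaps ANCOVA for a rank-sum test with no baseline term, so a disagreement need not be due to the outlier

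*Combined protocol and SAP*

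**What the plan says.** Section 5a (Quantitative Data) covers seven continuous outcomes: psychological community integration, self-esteem, social connectedness, hope, perceived housing quality, psychiatric symptoms and engulfment. The first two belong to the primary outcomes.

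- Main analysis: "Differences with 95% confidence intervals in continuous outcomes at 18 months" "will be estimated using Analysis of Covariance (i.e., linear regression models"), "including an indicator of intervention group and the baseline value of the outcome". No other covariate is named.
- Outlier check: "We will perform regression diagnostics and will repeat analyses using the non-parametric Wilcoxon" "rank-sum test if there are extreme outliers or influential observations".
- Count outcome, in the next sentence: "Groups will be compared with respect to count outcomes at 18 months (physical community integration) using graphical tools and the non-parametric Wilcoxon" rank-sum test, with no baseline term mentioned.

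Three things are not stated: the scores that go into the repeated Wilcoxon test, the threshold that makes an observation extreme or influential, and which result prevails if the two differ.

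**The concern.** A sensitivity analysis is easiest to read when it changes one feature of the main analysis. The feature in question here is sensitivity to a few unusual observations. The rank-sum test deals with that, but it has no place for the baseline score. The most natural reading is a comparison of month-18 scores, because the sentence concerns outcomes at 18 months and the same test is used that way for the count outcome.

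If ANCOVA then shows a difference and the Wilcoxon test does not, the reader cannot tell whether the outlier produced the first result or the lost adjustment weakened the second. An effect on a primary outcome could be labelled as not robust to outliers for a reason unrelated to outliers. With 12 per arm, chance baseline imbalance can be large, so the adjustment matters. The results are meant to inform a larger trial, and a wrong label would carry over.

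**Working it through.** **Inputs from the documents.** N = 24, half per arm, so 12 v 12; ANCOVA with arm and baseline value; rank-sum repeat; analysis at 18 months. The plan gives no power, effect size, SD, correlation or dropout figure, so there is no stated figure to reproduce.

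**Assumptions.** SD 1; true effect 0.8 SD; correlation rho between baseline and month 18 varied; no dropout; two-sided 5%, as the 95% intervals imply; Wilcoxon applied to month-18 scores.

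**Step 1: what the baseline term is worth.**
- Unadjusted SE = sqrt(2/12) = 0.408 SD.
- Adjusted SE = 0.408 × sqrt(1 − rho²). At rho 0.7 this is 0.408 × 0.714 = 0.292 SD.
- The SE of the chance baseline imbalance is also 0.41 SD. An imbalance of 0.5 SD shifts the unadjusted comparison by rho × 0.5: 0.15 SD at rho 0.3, 0.25 at 0.5 and 0.35 at 0.7.

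**Step 2: separate the two changes with no outlier present.** The simulation used 5,000 trials per scenario and normal scores. Entries are the percentage of trials in which two analyses disagree on p < 0.05.

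| rho | ANCOVA v Wilcoxon | Baseline dropped only (ANCOVA v t-test) | Ranks only (t-test v Wilcoxon) | ANCOVA v rank ANCOVA |
|---|---|---|---|---|
| 0 | 10 | 7 | 8 | 8 |
| 0.3 | 13 | 10 | 7 | 8 |
| 0.5 | 21 | 18 | 8 | 10 |
| 0.7 | 36 | 32 | 8 | 12 |
| 0.8 | 47 | 43 | 8 | 11 |

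Rank ANCOVA regresses the rank of the month-18 score on arm and the rank of the baseline score. From rho 0.5 upward, most of the disagreement comes from losing the baseline term. At rho 0 to 0.3 the two sources are of similar size.

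**Step 3: datasets in which the check would be used.** The assumed trigger is an externally studentised residual above 3 or Cook's distance above 0.5. Errors are heavy-tailed (t with 3 df, scaled to unit variance). Results are for triggered datasets.

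| rho | Power: ANCOVA / Wilcoxon / rank ANCOVA | Disagrees with ANCOVA: Wilcoxon / rank ANCOVA |
|---|---|---|
| 0.3 | 54% / 63% / 68% | 19% / 17% |
| 0.5 | 62% / 57% / 73% | 25% / 16% |
| 0.7 | 74% / 49% / 78% | 37% / 14% |

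Repeat runs of 4,000 to 6,000 trials per scenario agree within about three percentage points.

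**Step 4: how often the check fires.** Under that trigger it fires for one outcome in about 23% of normal-error datasets and 60% of heavy-tailed ones. With a stricter cut-off (studentised residual above about 3.5, or Cook's distance above 1) the figures are about 6% and 39%. For at least one of seven outcomes, treated as independent with normal errors, 1 − 0.77^7 = 84% under the first trigger and 1 − 0.94^7 = 35% under the stricter one.

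**Step 5: error rate of the alternative.** With no true effect, rank ANCOVA rejects in about 4 to 6% of all datasets. In triggered normal-error datasets alone it rejects in about 6 to 6.5%, which favours running it every time rather than only when a diagnostic fires.

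**The case against.** Four points on the other side deserve weight.

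- A reader might infer that ANCOVA is abandoned once an outlier appears. The text does not support that: it says analyses are repeated, and nothing withdraws the ANCOVA estimates. The problem is how to read the second result, not the loss of the first.
- A reader might take it as settled that the Wilcoxon test uses raw month-18 scores. That is the natural reading, but it is not stated. Change scores would keep part of the baseline information: at rho 0.7 with no outlier, Wilcoxon power is 64% on change scores and 42% on month-18 scores. At rho 0.3 the order reverses (31% v 42%), so the choice has to be written down.
- A reader might conclude that the planned test is simply inferior, or that the check will fire constantly. Neither follows. With heavy tails and rho 0.3 the Wilcoxon test has more power than ANCOVA (63% v 54%), so at low correlation it does its job. The firing rate rests on a threshold that the plan does not set.
- No decision rule or claim of power depends on this check. Section 5a says that results will be read with caution and used to generate hypotheses.

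All four stand, and they limit the size of the point. They do not remove it: whatever scores are entered, a rank-sum test has no baseline covariate, and caution in interpretation does not tell the reader which of two changes caused a disagreement.

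**Conclusion.** The point holds as a minor one. The outlier check for the seven continuous outcomes mixes robustness with loss of baseline adjustment, so a disagreement with ANCOVA cannot be put down to the outlier. The extra disagreement, compared with a rank method that keeps the baseline, is about 2 percentage points at rho 0.3 (19 − 17), 9 at 0.5 (25 − 16) and 23 at 0.7 (37 − 14). In these heavy-tailed scenarios rank ANCOVA also has more power than the planned test at each correlation shown; at rho 0 the two are equal, at 66%.

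These figures rest on an assumed effect of 0.8 SD, an assumed error shape, an assumed trigger, no dropout and month-18 input. The documents give none of the quantities needed to narrow the range.

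**What to change.** In section 5a, for the continuous outcomes only:

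1. State that the ANCOVA difference with its 95% confidence interval is the main result in every case.
2. Replace the Wilcoxon repeat with a robust check that keeps the baseline value, for example rank ANCOVA.
3. Run it for all seven outcomes as a sensitivity analysis, whatever the diagnostics show. No threshold then has to be defined.

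If the team prefers to keep the Wilcoxon test, the plan should at least state its input and the trigger, and add a baseline-adjusted check beside it.

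The cost is one sentence and a few lines of code, with no new data. Two limits remain: rank ANCOVA gives a test rather than a difference on the original scale, and it will still disagree with ANCOVA in roughly 14 to 18% of triggered heavy-tailed datasets. Conflicting results become fewer and easier to interpret, but they do not disappear.
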